9.1.1. Site Selection visit

Depending on the prospective clinical investigation site's experience with the specific investigational device, an on-site qualification or site selection visit shall be performed during which the feasibility of the clinical investigation requirements will be discussed and common agreement between sponsor and principal investigator shall be reached. This visit may also be replaced by one or more phone calls if the Principal Investigator is known to the sponsor.

9.1.2. Site Initiation visit

Before initiation of the clinical investigation, sponsor must be provided with key personnel signed and dated curriculum vitae (not more than two years old) and documentation of current GCP training (within the last two years) to verify their qualifications.

All clinical investigation sites will get an initiation visit during which full training on all aspects of the clinical investigation will be provided. This visit can be done on-site or remotely.

9.1.3. Site Monitoring visit(s)

The site dedicated monitor is to ensure adherence to the clinical investigation plan, accurate data recording on the eCRFs and to monitor recruitment rates and adherence to follow-up schedules. The Principal Investigator shall permit and assist the monitor to carry out verification of completed eCRFs against data in the source documents.

The Principal Investigator can delegate tasks to his/her personnel, however the role and time period of involvement for each clinical site personnel must be documented on the delegation log. Training for all delegated site personnel will be documented on the training log before any involvement with the clinical investigation.

The monitor shall inform the sponsor about any problems relating to facilities, technical equipment, or medical staff at the clinical investigation site. During the clinical investigation, monitors shall check that appropriate written informed consents have been obtained. The monitor shall also be responsible for notifying such deficiencies in writing to the Principal Investigator and convene with the clinical investigation site personnel appropriate and timely corrective actions.

The sponsor, or delegate, will provide clinical monitoring, including review of eCRF with verification to the source documentation, as defined in the monitoring plan. The monitor shall make written reports to the sponsor, after each visit and provide written action items if any, to the Principal Investigator or clinical investigation site personnel.

Periodic monitoring visits (remote or on-site) will be performed as soon as reasonable possible, after the site has enrolled the first subject in the investigation. A final monitoring visit will be performed after all subjects on site have completed the investigation.

A remote, centralized review of the data entered in the eCRF and the Subject's Clinical Trial App, will be performed by Coloplast CM throughout the conduct of the investigation. See section 9.3.

9.2. Source data verification

A source document is a document in which data collected for a clinical investigation is first recorded. This data is usually later entered in the eCRF. Source documents are defined as "original documents, data, and records". Source documents contain source data, which is defined as all information in original records and certified copies of original records of clinical findings, observations, or other activities in a clinical trial necessary for the reconstruction and evaluation of the clinical investigation.

All documents and data related to the clinical investigation handled by site personnel, shall be produced, and maintained in a way that assures reliability, integrity, control, and traceability, and shall be appropriately stored to provide a complete history.

The Principal Investigator shall ensure the accuracy, attribution, completeness, legibility, and timeliness of the data reported to the sponsor in the eCRFs and in all required reports. All printed copies of electronic source documents shall be certified, as indicated by a dated signature by the investigational site personnel at the time the document is printed. Special requirements should be applied to the capture, review, and retention of electronic source data, to ensure reliability, quality, integrity, and traceability.

The data reported in the eCRFs shall be derived from source documents and be consistent with these source documents, and any discrepancies shall be explained in writing. In some cases, the eCRF can serve as the source document and this must be documented on the Source Data Specification Form. The Source Data Specification Form must be completed at the initiation visit detailing the location of the source data for each data point.

Only the Principal Investigator, or designee, and the sponsor representatives will have access to all the eCRFs. The subject will have access to questionnaires and diaries completed in the Clinical Trial App.

9.3. Remote monitoring

Remote or centralized monitoring is a remote evaluation carried out by sponsor personnel or representatives (e.g., data management personnel, statisticians, or clinical monitors) at a location other than the site(s) at which the clinical investigation is being conducted. Remote monitoring processes can provide many of the capabilities of on-site monitoring as well as additional capabilities.

In addition to onsite monitoring visits, remote monitoring of the data entered in the e-CRF system could be used to achieve the following:

- Conduct activities such as: standard checks of range, consistency, and completeness of data and checks for unusual distribution of data, such as too little variance)
- Special attention will be given in case of frequent data anomalies or errors, protocol violations or excessive dropouts.
- Augment on-site monitoring by performing monitoring activities that can only be accomplished using centralized processes (e.g., statistical analyses to identify data trends not easily detected by on-site monitoring)
- Monitor data quality through routine review of submitted data in real-time to identify missing data, inconsistent data, data outliers, and potential protocol deviations that may be indicative of systemic and/or significant errors in data collection and reporting at the site.
- Verify source data remotely, provided that both source data and eCRFs can be accessed remotely.
- Conduct aggregate statistical analyses of study data to identify subject data that are outliers relative to others and to evaluate individual subject data for plausibility and completeness.
- Conduct analyses of site characteristics, performance metrics (e.g., high screen failure rates, high frequency of eligibility violations, and delays in reporting data), and clinical data to identify early on corrective actions needed for characteristics correlated with poor performance or noncompliance.

10. Statistical considerations

10.1. Statistical design, method, and analytical procedures

The primary objective will be evaluated by analysing the primary endpoint. The analyses of the exploratory endpoints [REDACTED] will be used to further evaluate and explore the primary objective. The secondary objective will be evaluated by analysing the secondary endpoint (the DLQI score) and further explored by analysing the DLQI sub-scale.

All baseline measurements, endpoints and assessments will be summarized by descriptive statistics and/or listed. Endpoints and assessments will be summarized by product and product type (1-piece or 2-piece). Descriptive statistics for continuous variables are presented with N, Mean, SD (standard deviation), Median, Min and Max, where N denotes the number of subjects contributing with non-missing data. For discrete variables, descriptive statistics are presented with N and percentage, where percentage is based on the total number of subjects/observations with non-missing data.

The pass criteria for the study is based on the result from the analysis of the primary endpoint and therefore no adjustment for multiple testing will be applied.

All statistical analyses are made with SAS version 9.4 (SAS Institute Inc., Cary, NC)

10.1.1. Definition of analysis populations

Intention to Treat (ITT), Safety and Per Protocol (PP) populations will be defined at a formal data review meeting before database lock. As a minimum, the data manager, the clinical manager and the statistician will be involved in the classification of subjects.

The ITT population (full analysis set) will be constituted by all randomised subjects with valid informed consent who have been exposed to at least one product, with information on at least one product with respect to either primary or secondary endpoints.

The PP population will constitute a subset of ITT subjects:

- who fulfill the inclusion/exclusion criteria
- where the primary endpoint, the decision tree score, is present in at least one of the steady state periods

- who have not used another product other than the randomized product for more than 3 days in a row at steady state
- who do not have a major deviation, as defined in section 13.0. Any exclusion of subjects from the PP/ITT population must be documented. Invalid individual data points may be omitted from analysis even though the corresponding subject is part of the ITT or PP population. Any exclusion of data points will be documented.

The Safety population will constitute by subjects who have given informed consent.

All statistical analysis will be based upon the ITT and PP population whereas adverse events and device deficiencies will be assessed based on the safety population.

Considering the data obtained it might be considered to make additional explorative analyses based on a subset of the ITT/PP population.

10.1.2. Analysis of the primary endpoint

Decision Tree (DT) score measured at each baseplate change at steady state will be analysed by a mixed repeated measures model using individual baseplate scores (on a scale from 0-3) as the observational unit. The model will consider that observations corresponding to different subjects are independent, whereas observations corresponding to the same subject are correlated. The correlation between observations corresponding to the same product can be larger than observations corresponding to different products. Hence the model includes a fixed effect of product (comparator product, test product), a fixed effect of product type (1- or 2-piece), a fixed interaction between product and product type, a fixed period effect, an interaction between period and product describing a possible carry-over effect, a random effect of subject, a random interaction effect of product and subject and a random residual error.

All combinations of differences between the two products will be estimated for both 1- and 2- piece products. Furthermore, differences for same product between product types will be estimated. If the interaction between product and product type is non-significant, the difference between the two products will be estimated.

As a sensitivity analysis, the primary analysis will be repeated including only subjects that have observations in both treatment periods. Hence the imputation of possible missing values can be evaluated.

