The duration of the test periods ($35^{-1/3}$ days) and number of visits should be adequate to assess data on the skin condition of the subjects. The investigational products are tested for $35^{-1/3}$ days in each study period to ensure that the skin will have time to adjust to new conditions, reach a steady state, and for the subjects to test the product for an adequate number of days to give a thorough evaluation of the products.

To account for a possible carry-over effect, the steady state period of the treatment period begins after two weeks of product use. It is anticipated that the skin will have adapted to the new product after two weeks.

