5.6. Randomisation Procedure

All subjects that meet the inclusion and exclusion criteria will be randomised to one of two treatment sequences. Both sequences examines the non-CE marked investigational product and the CE-marked comparator investigational product. The two sequences are:

- First sequence: The non-CE marked investigational product, then the CE marked comparator investigational products.
- Second sequence: The CE marked comparator investigational product, then the non-CE marked investigational product.

Randomization will be centralized using [REDACTED]

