10.1.3. Analysis of the secondary endpoints

The total Quality of Life (DLQI) score from Visit 2 and 3 will be analysed by a linear mixed model similar to the model for the primary endpoint, except that the random interaction effect of product and subject is not included, as there is only one measurement per subject for each product.

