10.2. Sample size

The Decision Tree (DT) score will be calculated at each baseplate change. A Severe score is equal to 3 whereas Moderate is 2, Mild is 1 and Not treatment required is 0. It is assumed that data are distributed in all 4 categories and therefore can be analysed by a model assuming normally distributed data.

The sample size calculation is based on a simplified linear mixed model with no effect of product type and no period effect. The model includes a fixed effect of product (comparator and test product), a random effect of subject and a random interaction effect of product and subject. As the sample size does not distinguish between product type it is assumed that both 1- and 2-piece users uses approximately 10 baseplates in the steady state period. This means, the power of the analysis might be in favour of 1-piece users if the final model is not combined as 1-piece users might use more products.

Based on data (PP population) from the previous CP288 investigation, it is assumed that the total standard deviation of the primary endpoint is 1.1 and that the total variation 1.1² is divided so that:

- a random effect of subject accounts for 46% of the total variation
- a random interaction effect of product and subject accounts for 9%
- and the residual accounts for 45% of the total variation

In the below table the needed sample size is calculated by simulation for varying values of the true difference between comparator and test product regarding mean DT score and for different values of the power to demonstrate that the difference is significantly different from 0.

Table 2: Subjects needed for comparing mean DT score (scale 0-3) between two products

True Difference	Reduction in mean if the mean for the comparator is 2.0 as for [REDACTED] in CP288	Power			
		0.8	0.85	0.9	0.95
0.2	10%	64	>70	>70	>70
0.3	15%	30	35	40	50
0.4	20%	<20	20	24	30
0.5	25%	<20	<20	<20	20

Based on interpolation between the numbers in the table, 33 subjects should test each product to ensure a power of 96%, if the true difference between the comparator product and a test product is 0.4 (clinically relevant difference according to the validation of the DT score). Correspondingly, 33 subjects will ensure a power of 83% if the true difference is 0.3 (still within the 95% confidence interval for the clinically relevant difference according to the validation of the DT score). 1-piece and 2-piece users will be evaluated separately (in a

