10.3. Level of significance and power

A two-sided significance level of 5% will be applied. For a description of the power see section 10.2 above.

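### Does the period-by-product term in the primary model, which is aliased with sequence, cost the crossover its power?

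*Combined protocol and SAP*

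**What the plan says.** Section 5.6 sets up a two-sequence, two-period crossover: "All subjects that meet the inclusion and exclusion criteria will be randomised to one of two treatment sequences", test product first or comparator first. The primary model in section 10.1.2 has fixed effects of product, product type, product by product type, period, and "an interaction between period and product describing a possible carry-over effect". It has random effects of subject and of product by subject. The section asks for product differences within 1-piece and 2-piece users, differences between types for the same product, and an overall product difference if the product-by-type interaction is not significant. It gives no rule that depends on the period-by-product term.

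Section 5.1 deals with carry-over by design: "To account for a possible carry-over effect, the steady state period of the treatment period begins after two weeks of product use". For DLQI, section 10.1.3 says the score "will be analysed by a linear mixed model similar to the model for the primary endpoint", so that model inherits the term. On power, section 10.2 says: "The sample size calculation is based on a simplified linear mixed model with no effect of product type and no period effect".

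**The concern.** Two sequences by two periods give four cell means. An intercept, product, period and their interaction use up all four, so the interaction labelled as carry-over is also the difference between the sequence groups. It cannot be told apart from a chance imbalance between those groups or from a product effect that truly differs by period.

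The plan also does not say whether the product difference is averaged over the periods or read within one. Read at period 1, it compares different subjects and loses the within-subject precision behind every power figure in section 10.2. The pass criterion in section 10.4 rests on this one difference, so a fall from 82% to 16% power would be serious.

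**Working it through.** **Inputs.** Section 10.3: "A two-sided significance level of 5% will be applied". Section 10.2: "it is assumed that the total standard deviation of the primary endpoint is 1.1", so the total variance is 1.21. Also from 10.2: "a random effect of subject accounts for 46% of the total variation", 9% is product by subject, 45% is residual, and there are about 10 baseplates per steady-state period. Sample sizes are 66 completers and 82 randomised. Assumptions: 1:1 allocation to sequence (the readable text gives no ratio) and 10 baseplates for everyone.

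Variance components:
- subject: 0.46 × 1.21 = 0.5566
- product by subject: 0.09 × 1.21 = 0.1089
- residual of a mean of 10: 0.45 × 1.21 / 10 = 0.05445

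**1. The plan's own power.** The variance of a within-subject product difference is 2 × (0.1089 + 0.05445) = 0.3267.

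| Subjects | True difference | Stated | Normal | t |
|---|---|---|---|---|
| 66 | 0.2 | 82% | 81.1% | 80.0% |
| 33 | 0.3 | 83% | 85.4% | 83.2% |
| 33 | 0.4 | 96% | 98.0% | 97.4% |

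Each stated figure is matched to within two points by at least one version, so the inputs are read correctly.

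**2. Aliasing.** Code product t, period p and sequence s as 0/1. Over the four cells, s = t + p − 2tp. The columns {1, t, p, tp} have rank 4, and adding s leaves rank 4. The aliasing is exact.

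**3. Product difference averaged over periods, term included.** This is half the difference between the two sequence groups' mean period differences: SE = ½ × √(2 × 0.3267 / 33) = 0.0704. The model without the term gives √(0.3267 / 66) = 0.0704. Power at 0.2 is Φ(0.2/0.0704 − 1.96) = 81% in both. The reason is simple: with complete data every subject has both products and both periods, so subject totals hold no information on product, and the term only absorbs a difference in totals.

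**4. With dropout.** Generalised least squares with 82 subjects, 16 of them contributing period 1 only, gives SE 0.0696 with the term and 0.0694 without. Power at 0.2 is 82% in both.

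**5. Product difference read at period 1.** The variance of a subject's period mean is 0.5566 + 0.1089 + 0.05445 = 0.720. SE = √(0.720 × 2 / 33) = 0.209, and the variance ratio to step 3 is (0.209/0.0704)² ≈ 8.8. Power with 66 subjects is 16% at 0.2, 30% at 0.3 and 48% at 0.4. With 33 subjects it is 17% at 0.3. A separate carry-over covariate that is non-zero only in period 2 gives the same SE.

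**6. The carry-over estimate itself.** The variance of a subject's total over the two periods is 4 × 0.5566 + 2 × 0.16335 = 2.553. SE = √(2 × 2.553 / 33) = 0.393, so the 95% half-width is 1.96 × 0.393 = 0.77 (0.79 with a t quantile). Power to detect a carry-over of 0.4 is 17%. This is on the scale of subject totals: a carry-over of size L shifts the averaged product difference by L/2, so on the product scale the half-width is about 0.39, close to the 0.4 that section 10.2 calls clinically relevant.

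**The case for a change.** The best case for a change is that the plan is silent where it could be explicit. Section 10.1.2 gives a rule for the product-by-type interaction and none for period by product. It does not say the product difference is averaged over periods, nor what follows if the carry-over p-value is small. In an open-label trial with a single pass criterion, that leaves room to choose once the data are seen, and one sentence would close it.

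The silence is real, but the text points one way. The contrasts listed in 10.1.2 are by product and product type, and none is within a period. A bare product coefficient in a model with both interactions would belong to one type and one period, so it could not supply the differences requested for both types. Estimated contrasts are needed, and the usual least-squares means average over periods. The plan describes no two-stage procedure in which the carry-over test selects the analysis. Under section 5.7 the statistician also stays blinded until database lock.

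It is also true that the term removes no carry-over bias from the averaged difference. Deleting it removes none either. The protection is the two-week lead-in, which section 5.1 already states. For DLQI, the questionnaire covers the last week of a period of about 35 days, so it too falls after the lead-in.

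**Conclusion.** The aliasing is exact, and the term is a poor measure of carry-over (SE about 0.39). The feared loss of power does not follow. The ordinary product difference, averaged over periods, keeps SE 0.070 and about 81% power at 0.2 with 66 completers, in line with the stated 82%, whether or not the term is in the model. With expected dropout the two versions differ by 0.0002 in SE. The drop to 16% at 0.2 (48% at 0.4) requires a contrast that the plan does not specify.

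Deleting the term, or writing down the averaging, would change no estimate, test or decision. This is a gap that an analyst fills in the standard way, so the plan can stand. The conclusion rests on the section 10.2 variance components, 10 baseplates per subject per period and 1:1 allocation. With complete data and equal baseplate counts, the agreement between the two models does not depend on the allocation ratio, for the reason given in step 3.

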4.8. Total number of investigational products intended for the clinical investigation

The subjects will be included for $35^{-1/3}$ days per test period, for approximately 70 days.

Subjects using 1-piece products are expected to change their products every day. Therefore, they are expected to use approximately 35 test products and 35 comparator products during their participation.

Subjects using 2-piece products are expected to change their products every two-three days. Therefore, they are expected to use approximately 20 test product baseplates and 20 comparator baseplates during their participation. Subjects using 2-piece products will be supplied with enough bags for the duration of the investigation.

5. Design of the clinical investigation

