combined model). Hence 33, 1-piece and 33, 2-piece users will be needed to complete the study. In case there are no significant difference between type of product the 66 users will be analysed in a reduced model. If the true difference is only 0.2 then 66 subjects should ensure a power of 82% to detect the difference as significantly different from zero but still within the 95% confidence interval for the clinically relevant difference. To take a potential drop-out (20%) into account it is recommended to include a total of 41 1-piece and 41 2-piece users, resulting in a total of 82 subjects.

If the recruitment target of 82 subjects is not reached within the timelines, the recommendation is to prolong the timelines to reach the recruitment target. This is to avoid a situation of not showing a significant result due to the power being too low.

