
Instructions
 
The following questions ask about the skin complications you experience around your stoma (from the stoma site to the edge of the stoma bag adhesive). Please answer each question thinking about the period since you last changed your product until now.
 
Question 4. Please rate on a scale from 0-10 how itchy the skin around your stoma has been at its worst since you last changed your product. (tick one box only)
 
 
 	0 No itch		1 Very mild itch		2		3		4		5		6		7		8		9		10 Worst possible peristomal skin itch	
 
					0 No itch		1 Very mild itch		2		3		4		5		6		7		8		9		10 Worst possible peristomal skin itch
	0 No itch		1 Very mild itch		2		3		4		5		6		7		8		9		10 Worst possible peristomal skin itch				

Please turn over
		
Modified OST PRO Version 12_0 Page 1
																							

Modified OST PRO Version 12_0 Page 2
		
Modified OST PRO Version 12_0 Page 2
																							

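### The planned comparison of 1-piece with 2-piece users on the Decision Tree score partly measures the length of the questionnaire's recall window, so it should be descriptive and should not decide pooling

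*Combined protocol and SAP*

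**What the plan says.** Section 10.1.2 analyses the Decision Tree score per baseplate in a mixed model. The terms are product, product type, their interaction, period, period by product, subject, product by subject, and residual. Besides the product differences within each type, it adds: "Furthermore, differences for same product between product types will be estimated". It then makes a single overall product difference conditional on a non-significant interaction of product with product type.

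Appendix 1 defines one input to the score as the highest of the pain, itching and burning ratings. In Appendix 4 the second block of items refers to the time since the previous product change, and the itch item asks "how itchy the skin around your stoma has been at its worst since you last changed your product". The bleeding, weeping and ulcer items in the first block refer to the moment of the change.

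On wear time, section 4.8 says: "Subjects using 1-piece products are expected to change their products every day". For the other type: "Subjects using 2-piece products are expected to change their products every two-three days".

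Section 10.2 words the pooling step differently from 10.1.2: "In case there are no significant difference between type of product the 66 users will be analysed in a reduced model".

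**The concern.** For an unchanged daily skin process, the worst value over two or three days cannot be lower than the worst value on any one of those days, and on average it is higher. The expected window is about one day for 1-piece users and two to three days for 2-piece users. The same question therefore asks for a different quantity in the two groups. The model has no term for wear time, so any resulting shift goes into the product-type effect and points towards worse skin in 2-piece users. This adds to the ordinary confounding of a comparison in which subjects bring their own product type.

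Two things are at stake. First, a recall artefact could be reported as a skin difference between product types. Second, the pooling sentence in 10.2, read literally, lets a type main effect decide whether the 66 users are analysed together. Such an effect could come from the questionnaire alone. Section 10.2 relies on those 66 users for its stated 82% power at a true difference of 0.2.

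**Working it through.** **Inputs from the plan.** Section 10.3: "A two-sided significance level of 5% will be applied". Section 10.2: "it is assumed that the total standard deviation of the primary endpoint is 1.1", so the total variance is 1.1² = 1.21. Also from 10.2: "a random effect of subject accounts for 46% of the total variation", 9% for product by subject, 45% residual, about 10 baseplates per subject at steady state, and 33 completers per type.

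**Reproducing the plan's power.** The paired difference of subject means has SD = √[2 × 1.21 × (0.09 + 0.45/10)] = √0.3267 = 0.572.

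- 33 subjects, true difference 0.3: 83.2% by the noncentral t (stated 83%).
- 33 subjects, 0.4: 97.4% by the noncentral t (stated 96%).
- 66 subjects, 0.2: 81.1% by the normal approximation, 80.0% by t (stated 82%).

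These agree within about 2 points, so the variance components are read as the plan intends. No stated figure is disputed.

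**Standard error of the between-type difference for one product.** The subject component does not cancel here:

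SE = √[2 × 1.21 × (0.46 + 0.09 + 0.45/10) / 33] = √(1.4399/33) = 0.209.

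Unequal baseplate counts hardly matter. Steady state is about 35 − 14 = 21 days. With 21 baseplates (daily change) against 21/2.5 = 8.4, the SE is 0.208.

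**Chance of a significant type difference when none exists**, for an assumed recall shift b: Φ(b/SE − 1.96) + Φ(−b/SE − 1.96).

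| Assumed shift b (score levels) | b/SE | Significant at nominal 5% |
|---|---|---|
| 0.05 | 0.24 | 5.7% |
| 0.1 | 0.48 | 7.7% |
| 0.2 | 0.96 | 16% |
| 0.3 | 1.44 | 30% |

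**Direction of the shift.** This was checked by simulating three 0–10 items with the same daily process in both groups. The assumptions, none from the documents, were subject mean 4, between-subject SD 2, day-to-day SD 0.5 to 2, and day-to-day correlation 0 to 0.8. The mean of the highest-of-three rating exceeds its 1-day value by 0.11 to 0.80 points for a 2-day window and by 0.18 to 1.21 points for a 3-day window. The sign is always upward. These are points on the 0–10 rating. Converting them to score levels needs the tree cut-offs, which are not shown.

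**Effect on the two pooling rules.** Let a shift b raise 2-piece scores on both products. The type main effect changes by b. The interaction, (test − comparator) in 2-piece users minus (test − comparator) in 1-piece users, changes by (b − b) − 0 = 0. The 10.1.2 rule is therefore largely insensitive to a common shift, while the 10.2 wording, taken literally, is exposed to it.

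**The case against.** The strongest reply is that nothing important rests on this contrast. It serves neither the primary nor the secondary objective, and section 10.4 bases success on test versus comparator alone. Section 10.1.2 only says that the between-type differences will be estimated and attaches no claim to them. That stands, and it limits the point to wording.

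A reader might infer that the artefact could block the pooled analysis. The documents do not support this as the operative reading. Section 10.1.2, which the change log says was revised in version 3.0 to clarify the primary analysis, conditions on the interaction, where a common shift largely cancels. The sentence in 10.2 may be shorthand for the same rule. Even if pooling were refused, the product difference would still be estimated within each type, for which 33 users per type were planned. What remains is that the two sections should say the same thing.

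A reader might also infer that the bias is as large as the 0.4 the plan calls clinically relevant. Shifts of about 0.16 to 0.45 levels can be generated, but only with invented cut-offs, a score driven by this rating alone, and a within-subject SD of 2 on the 0–10 items. With an SD of 1 the same approach gives about 0.10 to 0.24, and with 0.5 about 0.05 to 0.12. The bleeding, weeping and ulcer items refer to the moment of change, and discolouration comes from photographs; both would dilute these values further. The 0.4 also refers to test versus comparator, not to a contrast between types.

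Finally, the endpoint is defined per baseplate, so wear interval can be seen as part of how each type is used. That is a fair description of the endpoint, but it does not make a between-type difference interpretable as a difference in skin.

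**Conclusion.** The point holds in a limited form. The same-product comparison between types mixes recall length with skin condition and is tilted towards higher scores in 2-piece users, on top of the lack of randomisation. Its size cannot be derived from the documents. For assumed shifts of 0.05 to 0.3 levels, the false-positive rate of that contrast is about 6% to 30% instead of 5%.

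This rests on three assumptions:

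- The expected change intervals in 4.8 hold in practice, although the inclusion criteria allow either type up to four days.
- The pain and burning items share the recall window of the itch item, which is the only one legible; the block instruction suggests that they do.
- The highest-of-three rating determines the score level often enough to matter.

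A reader might infer that the primary test is biased too. The documents do not support that: test and comparator are compared within the same subject and product type, so the window is common to both as long as wear time is similar for the two products. The pass criterion is unaffected on the same condition.

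**What to change.** - In 10.1.2, replace the inferential between-type contrast with descriptive means by product and type. Report wear time by product and type alongside them, and state that the recall window differs between types. The wear-time table also lets a reader check that wear time was similar for test and comparator.
- In 10.2, reword the pooling sentence to match 10.1.2, so that combining the 66 users depends on the product-by-type interaction and not on a type main effect.
- Leave the within-type test-versus-comparator contrasts as they are.

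A model adjusting for time since the previous change should not be required. That covariate is closely tied to product type and may itself respond to skin condition, so it would not clearly recover a type effect.

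The cost is a wording change in two sections. The app is used at every change, so wear time should need no new data collection. What is lost is a formal between-type test that no objective needs.
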